13.0 DOCUMENT HISTORY

Version Number	Author(s)	Description
1.0	██████████	Initial version
2.0	██████████	
 • Section 6.2: Added PFS to testing procedures in Figure 1 • Section 7.2: removed “Only when the overdose is affiliated with adverse events, will this be considered an important protocol deviation” from the important protocol deviation criterion “Relative dose intensity >125% for study drug (programmatically derived). “ • Section 7.1: added “Baseline liver mets as per BICR (Yes, No)” and “number of disease sites per patient for target lesions’. • Section 7.4.3: removed “The number and percent of patients who took at least one subsequent post-study immune-oncology therapy, and post-study TKI therapy will be calculated and presented.” • Section 7.5.2: added sensitivity analysis of PFS accounting for two or more missing tumor assessments prior to PFS event (death or documented progression). • Section 7.5.4.3: Removed the sensitivity analysis of restricted mean of duration of response (this analysis will be done for DMC only). • Section 7.8.1: Removed sample level ADA analysis by analyte and by visit. Clarified that samples confirmed to be positive for anti-NKTR-214/anti-PEG, anti-IL-2 antibodies will be tested for neutralizing activity for IL-2 using a validated cell-based assay. Anti-nivolumab antibodies positive samples will also be tested for neutralizing activity for nivolumab using a validated cell-based assay. • Section 7.8.2: Clarified that infusion related reaction events that start after study drug administration on the same day or next day will be included. Clarified that pre-dose NKTR-214 RC and pre-dose NKTR-214 AC concentrations will be summarized by ADA status.

		
 • Section 8.1: add the following NKTR-214-related TEAE summaries: 
 ○ NKTR-214-related TEAEs presented by worst grade (any grade, grade 3-4, grade 5) by SOC and PT ○ Grade 3 or above NKTR-214-related TEAE by PT ○ Serious NKTR-214-related TEAE by PT ○ NKTR-214-related TEAE leading to death by PT ○ NKTR-214-related TEAE presented by worst grade (any grade, grade 3-4, grade 5) by SOC and PT (using an extended treatment-emergent period) • Section 8.2: Clarified that IMAEs will be summarized using the extended treatment-emergent period for each immune-mediated category for Arm A only. Re-challenge analysis is removed. • Section 8.3: Time to resolution analysis is removed. • Section 8.3.1: exposure adjusted analysis for ICE is removed. • Section 8.6.1: Table 7 (Criteria for Clinically Notable Vital Sign Abnormalities) is updated. • Section 9.2: The analysis on COVID 19 impacts on efficacy results may be performed if needed, and sections 9.2.1 (supplemental analysis on objective response rate) and 9.2.2 (supplemental analysis on overall survival) are removed. • Section 13: Document History section is added.
--	--	------------------------------------------------------------------------------------------------------------------------------------------------------------------------------------------------------------------------------------------------------------------------------------------------------------------------------------------------------------------------------------------------------------------------------------------------------------------------------------------------------------------------------------------------------------------------------------------------------------------------------------------------------------------------------------------------------------------------------------------------------------------------------------------------------------------------------------------------------------------------------------------------------------------------------------------------------------------------------------------------------------------------------------------------------------------------------------------------------------------------------------------------------------------------------------------------------------------------------------------------------------------------------------------------------------------------------------------------------------------------

15.0 APPENDIX

15.1 The Logrank Test for OS Analysis

Let T_1 denote the interim logrank test statistic with d_1 number of events and T_2 denote the logrank test statistic based on the cumulative data at final analysis with adapted d_2^* number of events. Then we calculate the incremental test statistic as following:

$$\tilde{T}_2^* = \frac{\sqrt{d_2^*}T_2 - \sqrt{d_1}T_1}{\sqrt{d_2^* - d_1}}.$$

The final combination test statistic (Lehmacher and Wassmer, 1999) with weight $\sqrt{\frac{2}{3}}$ and $\sqrt{\frac{1}{3}}$ can be written as $T_2^* = \sqrt{\frac{2}{3}}T_1 + \sqrt{\frac{1}{3}}\tilde{T}_2^*$. The overall Type I error rate is the probability of rejecting OS at either interim or final analysis under the null that there is no difference in survival between the treatment and control group (denoted as H_0). The critical value for the interim analysis is denoted as $\frac{z_{0.01}}{2} = \Phi^{-1}(1 - \frac{0.01}{2})$ (where Φ denotes the CDF for standard normal distribution) as two-sided 0.01 level of alpha is spent at this time. The critical value c for the final analysis is calculated so that the overall type I error rate is maintained at 0.049 (two-sided) or 0.0245 (one-sided). The probability can be calculated as follows:

$$0.0245 = P_{H_0}(T_1 > z_{0.01/2} \text{ or } T_2^* > c) = P_{H_0}(T_1 > z_{0.01/2}) + P_{H_0}(T_1 \leq z_{0.01/2} \text{ and } T_2^* > c)$$

Therefore, we need to find c such that $P_{H_0}(T_1 \leq \frac{z_{0.01}}{2} \text{ and } T_2^* > c) = 0.0195$. Because T_1 and T_2^* asymptotically follows standard normal distribution with correlation $\sqrt{\frac{2}{3}}$ (Wassmer, 2006), the critical value c can be found to be $z_{0.0231}$. This implies that the significant p-value will be 0.0231 (one-sided) or approximately 0.0462 (two-sided).

With similar arguments, if the overall type I error rate is to be maintained at 0.05 (two-sided) or 0.025 (one-sided), the nominal alpha for OS final analysis with weighted combination test will be 0.0236 (one-sided) or approximately 0.0472 (two-sided).

15.2 The Weighted Logrank Test for PFS Analysis

Let Z denote the weighted logrank test statistic with d_i number of events and Y_i number at risk. The test statistic Z can be written as

$$Z = \frac{\sum_{i=1}^D W(t_i) \left[d_{i1} - Y_{i1} \left(\frac{d_i}{Y_i} \right) \right]}{\sqrt{\widehat{Var}(Z)}}$$

where $\widehat{Var}(Z) = \sum_{i=1}^D W(t_i)^2 \frac{Y_{i1}}{Y_i} \left(1 - \frac{Y_{i1}}{Y_i} \right) \left(\frac{Y_i - d_i}{Y_i - 1} \right) d_i$ and $W(t_i) = \{\hat{S}(t_{i-1})\}^\rho \{1 - \hat{S}(t_{i-1})\}^\gamma$.

Considering the expected delayed effect on PFS, we select $\rho = 0$ and $\gamma = 1$ for the Fleming-Harrington test. Therefore, the weight $W(t_i) = 1 - \hat{S}(t_{i-1})$.

The PFS will be tested hierarchically given statistical significance of OS in both IMDC intermediate- or poor-risk (I/P-risk) population and all-risk population. The PFS interim and final analysis will be performed at the same time of OS interim or final analysis. The combination test statistic with weight $\sqrt{\frac{2}{3}}$ and $\sqrt{\frac{1}{3}}$ will be used in the final PFS analysis. For PFS, a 0.03 (two-sided) level of alpha will be spent at interim analysis. Following the same arguments as in Section 15.1, if the overall type I error is 0.049 (two-sided), the nominal alpha for the PFS final analysis will be 0.0323 (two-sided); if the overall type I error is 0.05 (two-sided), the nominal alpha for the PFS final analysis will be 0.0335 (two-sided).

15.3 Proof of Strong Family-wise Error Rate Control for the Four Primary Hypotheses and Two Key Secondary Hypotheses

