The potential of a delayed effect in immunotherapy interventions may cause a late separation in the PFS Kaplan-Meier curves and non-proportional hazards may be observed, as was seen for PFS in the Checkmate-214 study (Motzer 2018b). Thus, the primary analysis of PFS will account for the expected delayed effect and compare the two treatment arms via a stratified weighted logrank test (Harrington and Fleming 1982). The two-sided stratified weighted logrank p-value will be reported using G ($\rho = 0, \gamma = 1$) weights. The stratification factors will be the same as those used in the analysis of ORR (IMDC prognostic score and TKI choice) as defined in Section 6.5. At the final analysis, the primary analysis of PFS to claim statistical significance will be based on the weighted combination test of the stratified weighted logrank test statistic with pre-specified weights of $\sqrt{2/3}$ and $\sqrt{1/3}$ (Lehmacher and Wassmer, 1999). The details are presented in the Appendix.

The estimate of the PFS hazard ratio between treatment groups will be calculated using a stratified Cox proportional hazards model, with treatment as the sole covariate. The stratification factors will be the same as those used in the analysis of ORR (IMDC prognostic score and TKI choice) as defined in Section 6.5. Ties will be handled using the exact method. A two-sided 95% CI for the hazard ratio will also be presented. The Kaplan-Meier method will be used to further summarize PFS, including Kaplan-Meier curves, and medians with corresponding 95% CIs.

For the primary analysis of PFS, the censoring methods described in Table 3 will be used.

The conventional stratified logrank test with equal weights for every patient will be conducted as a sensitivity analysis.

The source of PFS event (progression or death) will be summarized by treatment group.

The status of patients who are censored in the PFS KM analysis will be tabulated for each treatment group using the following categories:

- On-study (on-treatment, in follow-up)
- Off-study (lost to follow-up, withdraw consent, never treated)
- No baseline tumor assessment
- No on-study tumor assessment and no death
- Received subsequent anticancer therapy

PFS per investigator assessment will also be analyzed as a sensitivity analysis. The PFS by investigator will be defined as in Table 3, and it will be analyzed in the same approach following the primary definition of PFS by BICR.

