15.3.1 Study Design

Figure 2 gives study design flow charts for ORR, OS, and Figure 1 shows the overall testing procedure for ORR, OS and PFS where PFS will be tested in IMDC I/P-risk and all-risk populations sequentially after statistical significance of OS in both populations. All p-values and testing levels are two-sided in this section and one-sided in Section 15.3.3. At interim analysis, if OS in IMDC I/P-risk population is not statistically significant at 0.01 level, then number of events in this population for the final analysis will be re-estimated based on the pre-specified adaptation rule. The final analysis will be triggered by the required number of events in the IMDC I/P risk population. At final analysis, if OS in IMDC I/P risk population is statistically significant (at 0.0462 level if ORR is not significant at IA and at 0.0472 level if ORR is significant at IA), then OS in IMDC all-risk population will also be tested at the same level as the IMDC I/P risk population. Given the statistical significance of OS in the IMDC all-risk population at FA, the key secondary endpoint of PFS by BICR in the IMDC I/P-risk population and the IMDC all-risk population will be test sequentially at level 0.0323 if ORR is not significant at IA and at level 0.0335 if ORR is significant at IA.

On the other hand, if OS in IMDC I/P risk population is statistically significant at 0.01 level at interim, then formal efficacy claim can be obtained, and no further testing will be performed for this population. At the same time, OS in the IMDC all-risk population can also tested at 0.01 level. If statistically significant, the key secondary endpoint of PFS by BICR in both populations will be tested sequentially at 0.03 level. Otherwise, if OS in all-risk population is not significant, number of events in this population for the final analysis will be re-estimated based on the pre-specified adaptation rule. The final analysis occurs when the adapted number of events in the IMDC all-risk population is achieved. The OS in IMDC all-risk population will be tested at 0.0462 level if ORR is not significant at IA and at 0.0472 level if ORR is significant at IA. And the key secondary endpoint of PFS by BICR in the two populations will be tested sequentially at level 0.0323 if ORR is not significant at IA and at level 0.0335 if ORR is significant at IA, given the statistical significance of OS in all-risk population at final analysis.

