15.3.2 Notation and Test Statistics

For OS in the IMDC I/P-risk populatio, let T_1 denote the interim logrank test statistic with d_1 number of events and T_2 denote the regular logrank test statistic based on the cumulative data at final analysis with adapted d_2^* number of events. Then we calculate the incremental test statistic following Wassmer (2006):

$$\tilde{T}_2^* = \frac{\sqrt{d_2^*}T_2 - \sqrt{d_1}T_1}{\sqrt{d_2^* - d_1}}.$$

The final weighted test statistic with weight $\sqrt{2/3}$ and $\sqrt{1/3}$ can be written as

$$T_2^* = \sqrt{2/3}T_1 + \sqrt{1/3}\tilde{T}_2^*.$$

Similarly for OS in the IMDC all-risk population, let T_1^a denote the interim logrank test statistic with d_1^a number of events, let T_2^{a*} denote the logrank test statistic based on the cumulative data at final analysis with d_2^{a*} number of events resulting from adaption in the IMDC I/P population and T_2^{a**} denote the logrank test statistic based on the cumulative data at final analysis with d_2^{a**} number of events resulting from adaption in the IMDC all-risk population. Then the corresponding incremental test statistics could be calculated as follows:

$$\tilde{T}_2^{a*} = \frac{\sqrt{d_2^{a*}T_2^{a*}} - \sqrt{d_1^aT_1^a}}{\sqrt{d_2^{a*} - d_1^a}} \quad \text{or} \quad \tilde{T}_2^{a**} = \frac{\sqrt{d_2^{a**}T_2^{a**}} - \sqrt{d_1^aT_1^a}}{\sqrt{d_2^{a**} - d_1^a}}.$$

The final test statistics can be written as

$$T_2^{a*} = \sqrt{2/3}T_1^a + \sqrt{1/3}\tilde{T}_2^{a*} \quad \text{or} \quad T_2^{a**} = \sqrt{2/3}T_1^a + \sqrt{1/3}\tilde{T}_2^{a**}.$$

Following a similar logic, we denote the interim test statistics for PFS in I/P and all-risk populations as Z_1 and Z_1^a , denote the final test statistics for PFS in both populations as Z_2^* , Z_2^{a*} based on adaption in the IMDC I/P population with event size d_2^{a*} , and Z_2^{**} and Z_2^{a**} based on adaption in the IMDC all-risk population with event size d_2^{a**} .

Further, let H_{01}^{OS} and H_{02}^{OS} denote the null hypotheses regarding the OS in IMDC I/P-risk and IMDC all-risk population, H_{01}^{ORR} and H_{02}^{ORR} denote the null hypotheses regarding the ORR in IMDC I/P-risk and IMDC all-risk population, and H_{01}^{PFS} and H_{02}^{PFS} denote the null hypotheses regarding the PFS in IMDC I/P-risk and IMDC all-risk population.

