 &P(\text{false rejection}) = P(\text{Reject } H_{0j}^{ORR} \text{ or } H_{01}^{PFS}) \\
 &= P(\text{Reject } H_{0j}^{ORR}) + P(\text{Reject } H_{01}^{PFS} \text{ but do not reject } H_{0j}^{ORR}) \\
 &\leq 0.0005 + P(T_1 > z_{0.005}, T_1^a > z_{0.005}, Z_1 > z_{0.015}) \\
 &+ P(T_1 > z_{0.005}, T_1^a \leq z_{0.005}, T_2^{a**} > z_{0.0462/2}, Z_2^{**} > z_{0.0323/2}) \\
 &+ P(T_1 \leq z_{0.005}, T_2^* > z_{0.0462/2}, T_2^{a*} > z_{0.0462/2}, Z_2^* > z_{0.0323/2}) \\
 &\leq 0.0005 + P(T_1 > z_{0.005}, T_1^a > z_{0.005}, Z_1 > z_{0.015}) \\
 &+ P(T_1 > z_{0.005}, T_1^a \leq z_{0.005}, T_2^{a**} > z_{0.0462/2}, Z_2^{**} > z_{0.0323/2}) \\
 &+ P(T_1 \leq z_{0.005}, T_2^{a*} > z_{0.0462/2}, Z_2^* > z_{0.0323/2}) \\
 &= 0.0005 + P(T_1 > z_{0.005}, T_1^a > z_{0.005}, Z_1 > z_{0.015}) \\
 &+ P(T_1 > z_{0.005}, T_1^a \leq z_{0.005}, T_2^{a**} > z_{0.0462/2}, Z_2^{**} > z_{0.0323/2}) \\
 &+ P(T_1 \leq z_{0.005}, T_1^a > z_{0.005}, T_2^{a*} > z_{0.0462/2}, Z_2^* > z_{0.0323/2}) \\
 &+ P(T_1 \leq z_{0.005}, T_1^a \leq z_{0.005}, T_2^{a*} > z_{0.0462/2}, Z_2^* > z_{0.0323/2}) \\
 &\leq 0.0005 + P(T_1 > z_{0.005}, T_1^a > z_{0.005}, Z_1 > z_{0.015}) \\
 &+ P(T_1 > z_{0.005}, T_1^a \leq z_{0.005}, Z_2^{**} > z_{0.0323/2}) \\
 &+ P(T_1 \leq z_{0.005}, T_1^a > z_{0.005}, Z_2^* > z_{0.0323/2}) \\
 &+ P(T_1 \leq z_{0.005}, T_1^a \leq z_{0.005}, Z_2^* > z_{0.0323/2}) \\
 &< 0.0005 + P(T_1 > z_{0.005}, T_1^a > z_{0.005}, (Z_1 > z_{0.015} \text{ or } Z_2^{**} > z_{0.0323/2})) \\
 &+ P(T_1 > z_{0.005}, T_1^a \leq z_{0.005}, (Z_1 > z_{0.015} \text{ or } Z_2^{**} > z_{0.0323/2})) \\
 &+ P(T_1 \leq z_{0.005}, T_1^a > z_{0.005}, (Z_1 > z_{0.015} \text{ or } Z_2^* > z_{0.0323/2})) \\
 &+ P(T_1 \leq z_{0.005}, T_1^a \leq z_{0.005}, (Z_1 > z_{0.015} \text{ or } Z_2^* > z_{0.0323/2})) \\
 &= 0.0005 + P(T_1 > z_{0.005}, (Z_1 > z_{0.015} \text{ or } Z_2^{**} > z_{0.0323/2})) \\
 &+ P(T_1 \leq z_{0.005}, (Z_1 > z_{0.015} \text{ or } Z_2^* > z_{0.0323/2}))
 \end{aligned}$$

$$\begin{aligned} & \text{(following similar logic in (1))} = 0.0005 + P(Z_1 > z_{0.015} \text{ or } \sqrt{2/3}Z_1 + \sqrt{1/3}T > z_{0.0323/2}) \\ & = 0.025 \end{aligned}$$

- Under partitioned parameter spaces 9, 10, 11, or 12 the false rejection rate is controlled by similar arguments as shown for partitioned parameter space 7 or 8.
- Under partitioned parameter spaces 13 or 14 (with $j=1$ or 2),
 $P(\text{False rejection}) = P(\text{Reject } H_{0j}^{ORR}) = 0.0005 < 0.025$

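### The stage-two PFS increment is never defined, and the only form the SAP points to, standardised by event counts, does not support 0.0323/0.0335 for a Fleming-Harrington (0,1) test

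*SAP*

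**What the plan says.** SAP 15.1 handles OS. It introduces an increment ("Then we calculate the incremental test statistic as following") equal to (sqrt(d2*) T2 - sqrt(d1) T1)/sqrt(d2* - d1), where d1 and d2* are event counts, and combines it with T1 using weights sqrt(2/3) and sqrt(1/3). The final OS levels follow from a bivariate normal with correlation sqrt(2/3).

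SAP 15.2 handles PFS. It defines the Fleming-Harrington statistic with rho = 0 and gamma = 1, so W = 1 - S(t-), and gives its variance sum. It then states: "For PFS, a 0.03 (two-sided) level of alpha will be spent at interim analysis". The final levels of 0.0323 (overall 0.049) and 0.0335 (overall 0.05) are obtained "Following the same arguments as in Section 15.1". No PFS increment is written. Section 7.5.2.1 says only that the final claim "will be based on the weighted combination test of the stratified weighted logrank test statistic with pre-specified weights of" the two fixed values, and sends the reader to the Appendix.

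SAP 15.3.2 is equally brief: "Following a similar logic, we denote the interim test statistics for PFS in I/P and all-risk populations as" a set of symbols. The final PFS statistics are labelled "based on adaption in the IMDC I/P population with event size" d_2^{a*}, or d_2^{a**} on the other path. The same section defines both symbols as all-risk OS event counts. No PFS event count or PFS information is defined.

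For parameter spaces 7 and 8, SAP 15.3.3 replaces the PFS increment by an independent standard normal variable. For spaces 9 to 12 it says that "the false rejection rate is controlled by similar arguments as shown for partitioned parameter space 7 or 8".

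**The concern.** A programmer who follows the SAP literally has one increment formula available, and it belongs to the ordinary log-rank test. There, information is roughly proportional to deaths, so scaling by counts gives a unit-variance increment that is independent of the interim statistic.

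For Fleming-Harrington (0,1) the information is a sum of squared weights. Those weights are near zero early and grow later, so information accrues later than events. Scaling by counts then gives an increment with the wrong variance that is correlated with stage one. The correlation of sqrt(2/3) behind 0.0323 and 0.0335 is lost, and so is the substitution step in 15.3.3.

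PFS is the alpha-controlled key secondary endpoint, and 15.3 is presented as a proof of strong family-wise control that includes it. Leaving the form open also leaves an analyst's choice on a confirmatory test.

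**Working it through.** **1. Reproduce the stated levels.** For a bivariate standard normal with correlation sqrt(2/3), solve P(Z1 > z1 or Z2* > c) = alpha/2.

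| Endpoint | Interim alpha | Overall alpha | Recomputed final level | SAP |
|---|---|---|---|---|
| OS | 0.01 | 0.049 | 0.04620 | 0.0462 |
| OS | 0.01 | 0.05 | 0.04725 | 0.0472 |
| PFS | 0.03 | 0.049 | 0.03229 | 0.0323 |
| PFS | 0.03 | 0.05 | 0.03359 | 0.0335 |

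The PFS levels are therefore right provided the increment is N(0,1) and independent of Z1.

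**2. Moments of the event-count increment.** Let f = d1/d2 be the event fraction and v = V1/V2 the Fleming-Harrington information fraction, so that corr(Z1, Z2) = sqrt(v). Then:

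- Var(inc) = (1 + f - 2 sqrt(f v))/(1 - f)
- Cov(inc, Z1) = (sqrt(v) - sqrt(f))/sqrt(1 - f)

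These equal 1 and 0 when v = f. Here v < f.

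**3. Inputs.** From the documents: 500 intermediate- or poor-risk patients, accrual of 28 per month, an interim at 156 deaths, and a final at 200 to 308 deaths. Assumed, because the documents give nothing: exponential PFS with median 6-15 months, censoring of 0-5% per month, and looks at month 28.5 and at month 35 (200 deaths) or 54 (308 deaths). These give f = 0.63-0.94 and v = 0.29-0.83.

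**4. Worked case, f = 0.88 and v = 0.73.**

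- Var(inc) = (1.88 - 2 sqrt(0.6424))/0.12 = (1.88 - 1.603)/0.12 = 2.31
- Cov(inc, Z1) = (0.8544 - 0.9381)/0.3464 = -0.242, so the correlation is -0.242/sqrt(2.31) = -0.16
- Var(Z2*) = 2/3 + 2.31/3 + 2 (sqrt(2)/3)(-0.242) = 1.21

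At the 0.0335 level (one-sided 0.01675), one-sided errors are:

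| f | v | Var(inc) | Corr with Z1 | Final look alone | Two looks (bound 0.025) |
|---|---|---|---|---|---|
| 0.63 | 0.29 | 2.09 | -0.29 | 0.0154 | 0.0273 |
| 0.88 | 0.73 | 2.31 | -0.16 | 0.0266 | 0.0368 |
| 0.94 | 0.83 | 2.89 | -0.14 | 0.0364 | 0.0464 |

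Over the full assumed range, Var(inc) is 2.1-3.1, the final look alone is 0.015-0.038, and the two-look error is 0.027-0.048. If the OS counts (156/200 or 156/308) are used as scaling instead, Var(inc) is 0.56-1.84 and the two-look error is 0.023-0.030.

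**5. Patient-level null simulation.** With a stratified Fleming-Harrington (0,1) test and 12,000 trials in each of four settings, the event-count increment had variance 2.27-2.94 and two-look one-sided error 0.031-0.048. The score increment (U2 - U1)/sqrt(V2 - V1) had variance 1.01-1.05 and error 0.0245-0.028.

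**6. With the OS gate.** In 15.3.1 PFS is tested once per path, after OS succeeds ("Given the statistical significance of OS in the IMDC all-risk population at FA, the key secondary endpoint of PFS by BICR"). Simulation of the three disjoint paths in 15.3.3 used OS levels 0.01/0.0472 and PFS levels 0.03/0.0335. It assumed an OS-PFS correlation of 0-0.6 and a correlation of 0.97 between the two populations for OS. One-sided PFS error with PFS counts:

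| OS effect | Gated error |
|---|---|
| HR 0.63 | 0.016-0.023 |
| HR 0.70-0.75 | 0.011-0.032 |
| Late effect (HR 0.85-0.95 before interim, 0.40-0.50 after) | 0.014-0.037 |

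The score-based increment gave 0.008-0.018 in the same runs. A separate patient-level simulation, 17,000 trials per setting with levels set for an overall 0.049, gave gated error 0.017-0.026 for the event-count form against a share of 0.0245.

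**The case against.** The strongest reply is that this is a missing definition and not a wrong method. What 15.2 carries over from 15.1 can be read as the solution for the critical value alone, which needs fixed weights and a standard normal increment but no particular scaling. 15.2 writes out the score and variance that a proper increment requires, and 15.3.3 assumes an N(0,1) increment, which only that form delivers. The event-size labels in 15.3.2 can be read as naming the path that triggered the look. The OS counts are the only counts in the notation, and scaling by them leaves the two-look error near 0.025. Finally, two-look figures are not the trial's error rate: with the OS gate and the design hazard ratio, PFS error stays below 0.025.

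Part of this stands. A score-based reading is possible and makes the levels correct. The gate does lower realised error, and the size depends on PFS assumptions that the documents do not supply. The rest does not dispose of the point. The SAP never states the score-based form, and the only formula it refers to breaks the step that its proof relies on. The written bound for spaces 7 and 8 drops the OS gate, so the gate cannot rescue it. Strong control must also hold for every OS configuration, including those where OS misses at interim and succeeds at the final analysis. The OS-count result near 0.025 does not validate that scaling: its increment variance still ranges from 0.56 to 1.84.

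**Conclusion.** The concern holds in conditional form. The PFS increment is undefined. If the referenced event-count form is used with PFS counts, the derivation of 0.0323/0.0335 and the bound for spaces 7 to 12 lose their basis, and strong control for PFS is not established. Under the stated assumptions the two-look one-sided error is 0.027-0.048 against 0.025. The OS-gated error is below 0.025 at an OS hazard ratio of 0.63 but up to 0.032-0.037 in some other configurations. This does not show that PFS error will exceed its level in this trial. ORR and OS control (spaces 1 to 6, 13 and 14) is untouched. It should be fixed before PFS is tested. Confidence is medium, because the size rests on assumed PFS medians, censoring and OS-PFS correlation.

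**What to change.** In SAP 15.2 and 15.3.2, define the PFS increment as (U2 - U1)/sqrt(V2 - V1). Here U and V are the stratified Fleming-Harrington (0,1) score and variance at the interim and final looks, each summed over strata. Combine it with Z1 using sqrt(2/3) and sqrt(1/3). Remove the OS event sizes from the PFS symbols, or state that they only identify which OS look triggered the analysis. Cite this definition in 15.3.3 where the standard normal substitution is made.

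The levels 0.0323 and 0.0335 can then stay, holding approximately. The OS formula does not change. The cost is a few lines of SAP text and code, with no effect on patients, data or timing.
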